## **10.5     Final Analysis Plan**

The ICH/FDA Guidance Document E9 (Statistical Principles for Clinical Trials) will be followed for all statistical content. For categorical data, summaries of frequencies and percentages will be

---

presented. Summaries for continuous data may include minimum, median, mean, SD, and maximum. All data will be summarized separately by dose group and study product. Listings of individual subject data will also be produced. Detailed summaries of the PK, immunogenicity and other analyses will be prospectively described in a statistical analysis plan (SAP) prepared by the SDCC statistician before unblinding of subjects. All final analyses will be performed by the SDCC statistician after the data are locked. Unless specified otherwise in the SAP, missing data will not be imputed.

All subjects receiving placebo will be combined across cohorts into a single placebo group for analysis. Missing data for outcome measures will not be imputed.

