### **10.5.1 Safety Analysis Plan**

Safety will be evaluated by presenting summaries of AEs, clinical laboratory evaluations (hematology evaluation, coagulation, chemistry panel, and urinalysis), vital signs, physical exam, and ECGs. Safety variables will be tabulated by dose group and presented for all subjects in the safety population. The safety population will include all subjects who receive any study product and will be grouped by treatment received.

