#### **10.5.1.1 Adverse and Serious Adverse Events**

Adverse events will be coded using MedDRA Version 25.1 or higher. The incidence of TEAEs will be presented by system organ class, high-level group term, and preferred term according to MedDRA, by relationship to the study product, by severity, and by whether or not they resulted in alteration of administration of or discontinuation of study product. In addition, the incidence of serious TEAEs and TEAEs leading to discontinuation of study product will be presented by system organ class, high-level group term, preferred term, and relationship to study product.

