#### **10.5.1.2 Clinical Safety Labs, Vital Signs, and Electrocardiograms**

Descriptive statistics for clinical laboratory test results, vital signs, and ECG intervals, including changes from baseline, will be presented by time point and dose group. Baseline is defined as the measurement closest to, but before, the administration of study product. If triplicate measurements were performed at the same visit, then baseline is the mean value of the measurements for the visit closest to, but before, administration of study product. Similarly, for analyses of change from baseline, mean values will be used in the case of replicate measurements at a single visit post baseline. Laboratory results and vital signs obtained after start of dosing will be graded according to criteria [Appendix C](#) and [Appendix D](#) for subjects who screened and enrolled prior to Protocol Version 11.0 and NCI CTCAE, Version 5.0 –

---

November 2017 for subjects who screen and enroll with Protocol Version 11.0 and summarized. Summaries of vital signs and ECG assessments will be analyzed at Screening and post dose using descriptive statistics.

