## Treatment Group

Participants will be enrolled and dosed in five dose-ascending cohorts, in which 2 participants will be randomized to placebo and 6 participants will be randomized to SAR440894. The ascending doses of SAR440894 will be 0.3 mg/kg, 1 mg/kg, 3 mg/kg, 10 mg/kg, and 20 mg/kg. Safety, PK, and immunogenicity results will be presented by treatment group. All participants assigned to placebo will be presented as pooled together for the purposes of these analyses. Treatment groups will be presented in the following order: SAR440894 0.3 mg/kg, SAR440894 1 mg/kg, SAR440894 3 mg/kg, SAR440894 10 mg/kg, SAR440894 20 mg/kg, and Placebo. Results from participants assigned placebo will not appear in the PK analyses.

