### 9.3. Adverse Events

An AE that occurs during or after the first study product infusion and through the final visit is defined as a TEAE. Only TEAEs will be documented as AEs in this study. AEs will be presented separately for participants who enrolled prior to Protocol v11.0 and participants who enrolled under Protocol v11.0.

Overall summaries of TEAEs will be given in **Table 40** and **Table 41** for participants enrolled before Protocol v11.0 and for participants enrolled under Protocol v11.0, respectively. These tables will include the number of participants with at least one AE, number of participants with at least one related AE, number of participants with at least one SAE, and the number of participants with laboratory abnormalities.

All TEAEs will be presented for participants enrolled before Protocol v11.0 in **Listing 13** and for participants enrolled under Protocol v11.0 in **Listing 14**. Participant listings of non-serious AEs of moderate or greater severity will also be reported separately for participants enrolled prior to Protocol v11.0 (**Table 54**) and for

participants enrolled under Protocol v11.0 (**Table 55**). Individual listings of TEAEs leading to study product discontinuation will be presented for participants enrolled prior to Protocol v11.0 (**Table 56**) and for participants enrolled under Protocol v11.0 (**Table 57**).

The following summaries for TEAEs will be presented by treatment group, MedDRA System Organ Class (SOC), High Level Group Term (HLGT) and Preferred Term (PT):

- The number of TEAEs and number and proportion of participants reporting a TEAE will be presented for participants enrolled before Protocol v11.0 (**Table 42**) and for participants enrolled under Protocol v11.0 (**Table 43**). The exact Clopper-Pearson 95% CI for the proportion of participants experiencing each SOC/HLGT/PT will also be presented.
- The number and proportion of participants reporting a TEAE will be presented by treatment group, SOC, HLTG, PT, maximum severity, and relationship to study product for participants enrolled before Protocol v11.0 (**Table 44**) and for participants enrolled under Protocol v11.0 (**Table 45**). Participants will only be counted once per PT and highest severity but may be counted for any relationship to study treatment.

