- The number and proportion of participants reporting a TEAE will also be presented by treatment group, SOC, HLTG, PT, and whether or not they resulted in alteration of administration of or discontinuation of study product for participants enrolled before Protocol v11.0 (**Table 46**) and for participants enrolled under Protocol v11.0 (**Table 47**).
- The number and proportion of participants reporting a TEAE leading to discontinuation of study product will be presented by treatment group, SOC, HLTG, PT, and relationship to study product for participants enrolled before Protocol v11.0 (**Table 50**) and for participants enrolled under Protocol v11.0 (**Table 51**). Participants will only be counted once per PT but may be counted for any relationship to study treatment.

Summaries of TEAEs will be presented graphically in bar charts by treatment group and SOC. For summaries of proportions of participants enrolled before Protocol v11.0 reporting a TEAE, denominators will be the number of participants in the Safety Population enrolled before Protocol v11.0 for each treatment group. For summaries of proportions of participants enrolled under Protocol v11.0 reporting a TEAE, denominators will be the number of participants in the Safety Population enrolled under Protocol v11.0 for each treatment group.

- The total number of related TEAEs reported will be presented by severity for participants enrolled before Protocol v11.0 (**Figure 13**) and for participants enrolled under Protocol v11.0 (**Figure 14**).
- The proportion of participants reporting a related TEAE will be presented by the maximum severity reported per SOC for participants enrolled before Protocol v11.0 (**Figure 15**) and for participants enrolled under Protocol v11.0 (**Figure 16**).

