#### 9.4. Deaths, Serious Adverse Events and Other Significant Adverse Events

The number and proportion of participants reporting an SAE will be presented by treatment group, MedDRA SOC, HLTG, PT, and relationship to study product for participants enrolled before Protocol v11.0 (**Table 48**) and for participants enrolled under Protocol v11.0 (**Table 49**).

Individual data listings of deaths and other SAEs will be provided for participants enrolled prior to Protocol v11.0 (**Table 52**) and for participants enrolled under Protocol v11.0 (**Table 53**). These listings will include participant ID, treatment group, AE description, SOC, HLTG, PT, duration of AE, reason reported as an SAE,

severity, relationship to treatment, alternate etiology if not related, action taken with study treatment, whether the participant discontinued due to the AE, and AE outcome.

Individual listings of SUSARs ([Table 58](#) and [Table 59](#)) and UPs ([Table 60](#) and [Table 61](#)) will also be presented for participants enrolled prior to Protocol v11.0 and for participants enrolled under Protocol v11.0, respectively. These listings will include participant ID, treatment group, AE description, SOC, HLG7, PT, duration of AE, severity, relationship to treatment, alternate etiology if not related, action taken with study treatment, whether the participant discontinued due to the AE, and AE outcome.

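### AE and SAE occurrence is tabulated only by protocol version, so no planned output gives the first primary endpoint for the whole Safety Population or for the single placebo group

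*SAP*

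**What the plan says.** **Protocol.** Section 10.5.1 states: "Safety variables will be tabulated by dose group and presented for all subjects in the safety population". Section 10.5 adds: "All subjects receiving placebo will be combined across cohorts into a single placebo group for analysis". Section 10.5.1.1 plans TEAE incidence and says that "the incidence of serious TEAEs and TEAEs leading to discontinuation of study product will be presented", with no mention of protocol version. Section 10.5.1.2 brings version in for one purpose: "Laboratory results and vital signs obtained after start of dosing will be graded according to criteria" that depend on the version under which the subject was enrolled. Section 8.1.1.1 also makes AE severity grading depend on version.

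**SAP.** Section 3.3 repeats the placebo rule: "All participants assigned to placebo will be presented as pooled together for the purposes of these analyses". Section 6.7 announces that safety data will be shown by version and gives two reasons. The grading scales differ, and so does the rule for which laboratory and vital-sign findings count as AEs. Section 9.3 then says "AEs will be presented separately for participants who enrolled prior to Protocol v11.0 and participants who enrolled under Protocol v11.0", and for the earlier stratum "denominators will be the number of participants in the Safety Population enrolled before Protocol v11.0 for each treatment group". Section 9.4 presents SAEs by term and "relationship to study product for participants enrolled before Protocol v11.0" in Table 48, with a twin, Table 49, for v11.0.

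**The concern.** The protocol leads a reader to expect one display of AE and SAE occurrence per dose group, one placebo column holding all placebo participants, and a total. The SAP instead gives two half-displays. In each, a dose group is compared with only the placebo participants enrolled under the same version, and the All Participants column is also confined to that version. In a study with six active participants per dose and ten on placebo, a further split makes already wide intervals wider. The two sets of exact intervals in Tables 42 and 43 cannot be merged into an interval for the whole group without going back to the counts.

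**Working it through.** **1. Planned sizes.** SAP Table 1 has five cohorts of 6 active and 2 placebo: 5 × 8 = 40 in all, 5 × 6 = 30 active, 5 × 2 = 10 placebo. These match the stated totals.

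**2. Search for a combined output.** Every AE and SAE display comes as a before-v11.0 and under-v11.0 pair: Tables 40–61, Listings 13–14 and Figures 13–16. The lists of tables, figures and listings hold no AE or SAE output for the whole Safety Population. SAP 6.2 mentions an end-of-study cumulative safety summary for the Safety Monitoring Committee, but no table is specified for it.

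**3. How far the SAP 6.7 reasons reach.**

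- *Severity grade:* the scales differ (three grades against CTCAE's five), so the split is justified.
- *Laboratory and vital-sign AEs:* the rule for what counts changed, so the split is justified.
- *ECG findings:* Protocol 8.5 and Appendix B apply different criteria by version. Appendix B's statement that sinus arrhythmia is not an AE applies only to subjects enrolled before v11.0. Caution is justified here too.
- *SAE occurrence:* the definition in Protocol 8.1.2 rests on outcome and has no version condition. Neither reason reaches it. (Only v11.0 of the protocol was available.)
- *Other AEs, regardless of grade:* the stated reasons concern grading and laboratory or vital-sign findings, so they do not reach these either.

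**4. Precision.** SAP 6.1 uses exact Clopper-Pearson intervals. With zero events in n participants, the 95% upper limit is 1 − 0.025^(1/n). The documents give no enrolment by version, so every split below is an assumption.

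| Group | Combined | Assumed split |
|---|---|---|
| Placebo | n=10: 30.8% | 5/5: 52.2% each |
| Placebo | n=10: 30.8% | 8/2: 36.9% and 84.2% |
| All participants | n=40: 8.8% | 20/20: 16.8% each |
| All participants | n=40: 8.8% | 32/8: 10.9% and 36.9% |
| One dose group | n=6: 45.9% | 3/3: 70.8% each |

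For example, 1 − 0.025^(1/10) = 0.308 and 1 − 0.025^(1/5) = 0.522. A dose group enrolled wholly under one version keeps n=6 and loses nothing.

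**5. A related slip.** The footnotes of Tables 40 and 41 define N as the Safety Population, while the titles and SAP 9.3 confine each table to one version. Taken literally, a one-version numerator would sit over the full denominator. Under the assumed 20/20 split, 2 of 20 (10%) would print as 2 of 40 (5%).

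**The case against.** The strongest reply is that the split is declared and explained in SAP 6.7, and that the protocol can be read as satisfied. Every participant appears in exactly one of two disjoint tables, and Protocol 10.5 combines placebo across cohorts without mentioning versions. Because the strata are disjoint, counts of any AE, related AE and SAE add directly from Tables 40–41, term-level counts from Tables 42–43, and SAEs by term from Tables 48–49. A percentage and exact interval follow from the sums. The study is descriptive, and the split sizes used above are invented.

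Most of this stands, and it sets limits on the point. Four stronger readings are tempting and are not supported:

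- *The SAP contradicts itself because SAP 6.7 says safety data are otherwise pooled.* That sentence concerns pooling across clinical sites and means apart from the version split just announced.
- *The split is a concealed departure from the protocol.* SAP 6.7 states it openly. It is only missing from the list of changes in SAP 15.
- *The split biases the result or loses data.* It does neither.
- *All AEs should simply be pooled.* Laboratory, vital-sign and ECG findings were not handled alike under the two versions, so a single unrestricted AE count would mix definitions.

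The reply does not explain why SAE occurrence should be split at all, or why the reader should have to assemble the primary endpoint by hand.

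**Conclusion.** The point holds in a limited form. No planned output gives a combined n, percentage or exact interval for the first primary endpoint in the Safety Population or in the single placebo group. The stated reasons support splitting severity and laboratory and vital-sign AEs, but not SAE occurrence. The consequence is weaker precision and harder reading of the primary endpoint. How much weaker depends on enrolment by version, which is unknown. If the ten placebo participants fell 5/5, a zero-event upper limit of 30.8% would be shown as 52.2% twice. If nearly all enrolment fell under one version, the larger stratum would lose little. The analysis remains valid without the change, but the change is worth making.

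**What to change.** Keep every version-specific table. Add one combined table by dose group, single placebo group and all participants, with n, percentage and exact Clopper-Pearson interval, for:

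1. any SAE and any related SAE;
2. any AE and any related AE, regardless of grade, excluding events that are solely a laboratory, vital-sign or ECG finding. A finding recorded as part of a diagnosis (Protocol 8.5) counts under that diagnosis.

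Fix the exclusion rule before unblinding, apply it to the reported terms of both strata with treatment hidden, and footnote that AE criteria differed by version. Correct the N footnotes of Tables 40 and 41 to name the stratum that each covers. Record both the version split and the added table in SAP 15.

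The cost is SAP wording, one or two more tables programmed from data already collected, and a short blinded review of AE terms. SAEs need no such review. Borderline terms such as fever or tachycardia will need the written rule.

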## 14.3 Safety Data

### 14.3.1 Displays of Adverse Events

**Table 40: Overall Summary of Adverse Events – Participants in the Safety Population Enrolled Prior to Protocol v11.0**

	SAR440894 0.3 mg/kg (N = xx)		SAR440894 1 mg/kg (N = xx)		SAR440894 3 mg/kg (N = xx)		SAR440894 10 mg/kg (N = xx)		SAR440894 20 mg/kg (N = xx)		Placebo (N = xx)		All Participants (N = xx)	
Participants a with	n	%	n	%	n	%	n	%	n	%	n	%	n	%
At least one adverse event														
At least one related adverse event	x	x	x	x	x	x	x	x	x	x	x	x	x	x
Mild (Grade 1)	x	x	x	x	x	x	x	x	x	x	x	x	x	x
Moderate (Grade 2)														
Severe (Grade 3)	x	x	x	x	x	x	x	x	x	x	x	x	x	x
At least one severe (Grade 3) unsolicited adverse event														
Related	x	x	x	x	x	x	x	x	x	x	x	x	x	x
Unrelated	x	x	x	x	x	x	x	x	x	x	x	x	x	x
At least one serious adverse event	x	x	x	x	x	x	x	x	x	x	x	x	x	x
At least one related, serious adverse event	x	x	x	x	x	x	x	x	x	x	x	x	x	x
At least one adverse event leading to discontinuation of study product b														
At least one adverse event leading to early termination b														
At least one laboratory abnormality														
At least one related laboratory abnormality														
At least one clinically significant laboratory abnormality c														
Related														
Unrelated														
At least one not clinically significant laboratory abnormality c														
Related														
Unrelated														

Notes: N = Number of participants in the Safety Population

a Participants are counted once for each category regardless of the number of events.

b As reported on the Adverse Event eCRF.

c As reported on the Local Laboratory Results eCRFs.

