	[SOC 1]	Any HLG	Any PT	x (x)	xx, xx	x
		HLG1	Any PT	x (x)	xx, xx	x
			[PT 1]	x (x)	xx, xx	x
	[SOC 2]	Any HLG	Any PT	x (x)	xx, xx	x
		HLG1	Any PT	x (x)	xx, xx	x
			[PT 1]	x (x)	xx, xx	x
SAR440894 0.3 mg/kg (N=X)	...		...	x (x)	xx, xx	x
...	...		...	x (x)	xx, xx	x
Placebo (N=X)	...		...	x (x)	xx, xx	x

Notes: N = Number of participants in the Safety Population enrolled before Protocol v11.0 in the specified treatment group.  
n=Number of participants reporting adverse events within each SOC/HLG/PT.  
A participant is only counted once per PT per treatment group.  
aExact Clopper-Pearson Confidence Interval.

Table with Similar Format:

**Table 43: Summary of Adverse Events by MedDRA System Organ Class, High Level Group Term and Preferred Term, and Treatment Group – Participants in the Safety Population Enrolled Under Protocol v11.0**

**Table 44: Adverse Events by MedDRA System Organ Class, High Level Group Term and Preferred Term, Maximum Severity, Relationship, and Treatment Group – Participants in the Safety Population Enrolled Before Protocol v11.0**

[Implementation Note: If there is only 1 PT for an SOC and HLGT, there will be no “Any PT” row. Likewise, if there is only 1 HLGT for an SOC, there will be no “Any HLGT” row.

Repeat for the following treatment groups: All Participants, SAR440894 0.3 mg/kg, SAR440894 1 mg/kg, SAR440894 3 mg/kg, SAR440894 10 mg/kg, SAR440894 20 mg/kg, and Placebo]

Treatment Group	MedDRA System Organ Class	MedDRA High Level Group Term	MedDRA Preferred Term	Severity	Related n (%)	Not Related n (%)	Total n (%)
All Participants (N=X)	Any SOC	Any HLGT	Any PT	Any Severity	x (%)	x (%)	x (%)
				Mild	x (%)	x (%)	x (%)
				Moderate	x (%)	x (%)	x (%)
				Severe	x (%)	x (%)	x (%)
	[SOC 1]	Any HLGT	Any PT	Any Severity	x (%)	x (%)	x (%)
				...	x (%)	x (%)	x (%)
		HLGT1	Any PT	Any Severity	x (%)	x (%)	x (%)
				...	x (%)	x (%)	x (%)
		HLGT1	[PT1]	Any Severity	x (%)	x (%)	x (%)
				...	x (%)	x (%)	x (%)
	...		...	...	x (%)	x (%)	x (%)
SAR440894 0.3 mg/kg (N=X)	...		...	...	x (%)	x (%)	x (%)
...	...		...	...	x (%)	x (%)	x (%)
Placebo (N=X)	...		...	...	x (%)	x (%)	x (%)

Notes: N = Number of participants in the Safety Population enrolled before Protocol v11.0 in each treatment group.

Participants are only counted once per PT and treatment group, in the highest reported severity. Participants may be counted for either or both Related and Not Related to study treatment.

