### 14.3.1.2 Unsolicited Adverse Events

**Figure 13: Frequency of Related Adverse Events by MedDRA System Organ Class and Severity – Participants in the Safety Population Enrolled Before Protocol v11.0**

[Implementation Note: This figure includes serious and non-serious unsolicited adverse events related to the study product. Note that this figure will present the number of events for each type of SOC. There will be one panel for each of the following groups: All Participants, SAR440894 0.3 mg/kg, SAR440894 1 mg/kg, SAR440894 3 mg/kg, SAR440894 10 mg/kg, SAR440894 20 mg/kg, and Placebo. Order SOCs alphabetically.]

[figure not shown]

[figure not shown]
Figure with Similar Format:

**Figure 14: Frequency of Related Adverse Events by MedDRA System Organ Class and Severity – Participants in the Safety Population Enrolled Under Protocol v11.0**

**Figure 15: Incidence of Related Adverse Events by MedDRA® System Organ Class and Maximum Severity – Participants in the Safety Population Enrolled Before Protocol v11.0**

[Implementation Note: This figure includes serious and non-serious unsolicited adverse events related to the study product. Note that this figure will present the number of participants with each type of SOC. A participant will only be counted once for the same SOC for the maximum severity reported.

There will be one panel for each of the following groups: All Participants, SAR440894 0.3 mg/kg, SAR440894 1 mg/kg, SAR440894 3 mg/kg, SAR440894 10 mg/kg, SAR440894 20 mg/kg, and Placebo. Order SOCs alphabetically.]

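### As literally worded, the counting rule for SAP Tables 44–45 fixes one severity per participant over all events before splitting by relationship, so the Related column can show a wrong severity or none

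*SAP*

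**What the plan says.** SAP section 9.3 introduces Tables 44 (enrolled before Protocol v11.0) and 45 (enrolled under v11.0) with the rule "Participants will only be counted once per PT and highest severity but may be counted for any relationship to study treatment". The footnotes of both shells repeat it in two parts: "Participants are only counted once per PT and treatment group, in the highest reported severity", followed by "Participants may be counted for either or both Related and Not Related to study treatment". The shells have Related, Not Related and Total columns. Their rows run from Any SOC through SOC and HLGT to PT, each with an Any Severity line and one line per grade. The rule is stated per PT only; nothing is said about the aggregate rows.

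Other displays treat related events as their own set:

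- Figures 15–16: "The proportion of participants reporting a related TEAE will be presented by the maximum severity reported per SOC". The Figure 15 shell confirms the restriction: "This figure includes serious and non-serious unsolicited adverse events related to the study product".
- Figures 13–14: "The total number of related TEAEs reported will be presented by severity".
- Tables 40–41 have severity lines under participants with at least one related event, with the note "Participants are counted once for each category regardless of the number of events".
- Tables 52–55 and Listings 13–14 show severity and relationship event by event.

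**The concern.** Protocol section 10.5.1.1 asks for the incidence of TEAEs by SOC, HLGT and PT, by relationship and by severity. Tables 44–45 are the only tables that cross severity with relationship at all those levels by dose. In a first-in-human study, a reader goes to the Related column to see how severe the drug-related events were.

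Under the rule as worded, an unrelated event can set the severity at which a related event is shown. The order of the two steps, maximum and split, decides whether the Related column describes related events.

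**Working it through.** The plan states no figure on this point, so there is none to reproduce.

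**1. What the words require.** The footnote allows one count per PT, at one severity. A maximum taken within each relationship column could put one participant at two severities for the same PT (mild under Related, severe under Not Related), which conflicts with a single count at the highest severity. The literal rule is therefore maximum over all events first, split second.

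**2. One participant, one row.** Take a related Grade 1 event and an unrelated Grade 3 event.

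| Reading | Related column | Not Related column | Total |
|---|---|---|---|
| Overall maximum, placed in both columns | Any 1, Severe 1, Mild 0 | Any 1, Severe 1 | Severe 1 |
| Overall maximum, placed only where it occurred | Any 1, no severity line | Any 1, Severe 1 | Severe 1 |
| Maximum within each column | Any 1, Mild 1 | Any 1, Severe 1 | Severe 1 |

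Only the third reading reports the related event at its own grade, with the Related severity lines adding up to Any Severity.

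**3. All pairs of one related and one unrelated event.** The Related column is wrong whenever the related event is the milder one: 3 of 3 × 3 = 9 severity pairs with three grades (Table 44), and 10 of 5 × 5 = 25 with five grades (Table 45). The Not Related column is wrong in the mirror-image 3 and 10. These are counts of configurations, not probabilities.

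**4. Size per participant.** Each cohort has 6 active participants: 1/6 = 16.7 percentage points. If all 10 pooled placebo participants fall in one of the two tables, 1/10 = 10.0 points. The shift is larger if a group is divided between Tables 44 and 45, and slightly smaller if dosed replacements enlarge it.

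**5. Frequency, as an illustration only.** Assume Poisson counts averaging 3 AEs per participant, 30% related, severity 75/20/5% mild/moderate/severe, all independent. Related events then average 0.9 and unrelated events 2.1.

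- P(at least one related) = 1 − e^(−0.9) = 0.593.
- Given that, worst related event moderate or worse: (1 − e^(−0.9 × 0.25))/0.593 = 0.340. Severe: (1 − e^(−0.9 × 0.05))/0.593 = 0.074.
- Any unrelated event moderate or worse: 1 − e^(−2.1 × 0.25) = 0.408. Severe: 1 − e^(−2.1 × 0.05) = 0.100.
- A worse unrelated event is present: (1 − 0.340) × 0.408 + (0.340 − 0.074) × 0.100 = 0.296.
- With the overall maximum placed in both columns, moderate or worse becomes 1 − 0.660 × 0.592 = 0.609 instead of 0.340, and severe becomes 1 − 0.926 × 0.900 = 0.167 instead of 0.074.

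That is the Any SOC row. The same formula gives 16% (2 AEs, 50% related) to 46% (5 AEs, 20% related) of participants with a related AE, and 9% to 14% at an average of 1 AE. At PT level, with the 3 AEs spread evenly over an assumed 10 to 30 PTs, it falls to about 4% to 1.4% of participant-PT cells containing a related event.

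**6. Agreement with Figures 15–16.** These take the maximum per SOC among related events only. The SOC rows of the Related column describe the same quantity, but under the literal rule they differ for every participant of the kind in step 2.

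**The case against.** The strongest reply is that the SAP never states the order of the two steps. Allowing a participant to be counted for any relationship can loosely be read as permitting a separate maximum in each column, which is the correct table. So a reader should not infer that the SAP deliberately prescribes the wrong order. That stands. The literal wording still points the other way, and two programmers could defensibly produce different tables.

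Other stronger inferences are not supported:

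- **The halting rules are affected.** Protocol section 8.6 applies them to accruing events, reviewed during the study by the site investigators, the Safety Review Committee, the data coordinating center and the medical monitor. Under SAP section 6.2, the final report containing Tables 44–45 follows database lock.
- **The severity of related events is lost.** Figures 13–16, Tables 52–55 and Listings 13–14 show it correctly. With six active participants per dose, each related event of moderate or greater severity can be found individually.
- **Tables 40–41 must match Tables 44–45.** Tables 40–41 count a participant once per category with no stated maximum-severity rule, so someone with mild and moderate related events can appear on both lines. They need not agree even after the fix. Figures 15–16 are the fair comparator.
- **The problem is frequent at PT level.** It needs the same PT twice in one participant, judged differently, with the unrelated occurrence worse.

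**Conclusion.** The point holds as a defect in the literal counting rule of one pair of descriptive tables. For a participant with related and unrelated events of different severity in the same row, following the text puts the milder event's column at a grade that did not occur there, or leaves it with no severity line. The example in step 2 needs no assumption about event rates.

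The size is 16.7 percentage points per misplaced participant in a dose group of 6. How many participants are affected cannot be taken from the documents, which give no AE rate, related fraction or severity mix. The percentages in step 5 rest on assumed values and on independence, which would overstate the problem if relatedness judgments tend to agree within a participant. They should not be quoted as expected results. The exposure lies mainly in the Any PT, HLGT, SOC and Any SOC rows. No test, sample size or dosing decision depends on these tables.

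**What to change.** Replace the counting sentence in SAP section 9.3 and the matching footnotes of Tables 44 and 45 with wording such as: within each PT, HLGT, SOC and Any row, a participant is counted once in the Related column at the highest severity among related events, once in the Not Related column at the highest severity among not-related events, and once in Total at the highest severity over all events; the Related and Not Related columns need not sum to Total.

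This makes the Related severity lines add up to Any Severity and aligns the SOC rows with Figures 15–16. The cost is one sentence, two footnotes and a small programming change. Data collection, conduct and sample size are unaffected.
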